Q1. What is the lung deposition behaviour of inhaled bronchodilator aerosols of different particle size within the airways of patients with chronic obstructive pulmonary disease (COPD)? How does this distribution compare to that observed in healthy subjects with no lung disease?

Q2. What is the effect of different patient inhalation flows on the lung deposition of different sized bronchodilator particles? Is there a specific particle size and inhalation flow to achieve optimal lung deposition in COPD patients?

Q3. Does the regional deposition and distribution of inhaled bronchodilator aerosols influence the clinical (physiological pharmacodynamic) and systemic (urinary pharmacokinetic) responses in COPD patients?

3. Study Design

This protocol has two studies: Lung DEPOSITION study (in COPD patients and Healthy subjects) and Lung PHYSIOLOGY study (in COPD patients and Asthmatics).

Each study (Lung DEPOSITION and Lung PHYSIOLOGY) will be a randomised, double-blind, cross-over study (6 monodisperse 'fine-mist' aerosol treatments, controlled against one polydisperse 'coarse-mist' pressurised metered dose inhaler (pMDI) visit). Treatments will be given as one-off dose-administration. There will be an interval of at least 5 days between each study visit.

The Lung DEPOSITION study will involve radiolabelled drug treatments (monodisperse aerosols only = 6 visits). All the treatments in the LUNG PHYSIOLOGY study will be non-radiolabelled.

4. Study Outcomes

Primary outcome:

Lung DEPOSITION study: The primary endpoint for aerosol deposition is penetration index (PI) calculated from planar-images, which will indicate differences in regional lung deposition as a function of particle size.

Lung PHYSIOLOGY study: The primary endpoints are multi-breath nitrogen washout (MBNW) indices of acinar airways (Sacin) and conducting airways (Scond), which will indicate differences in small (and large) airway physiology as a function of particle size.

Secondary outcomes:

The secondary outcome measures for both studies are: analysis of the lung physiology (MBNW, Impulse oscillometry (IOS), spirometry, body plethysmography) and urine pharmacokinetics (urine 0-30minutes, 0-24 hours, 30mins -24 hours)

5. Study Centre / Number of Patients / Recruitment

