Following inhalation, participants will be seated in front of a gamma camera and inhaled particle distribution will be assessed with planar imaging. Scintigraphic images of the posterior thorax, anterior thorax, and lateral oropharynx will be recorded, in sequence, with the patient repositioned between views. This will be completed within 5 minutes following the aerosol inhalation. Subjects will undergo a krypton-81m ventilation transmission scan to define their lung boundary.

Participants will then undergo non-invasive measures of pulmonary function and pharyngeal function including; spirometry, impulse oscillometry, and multi-breath nitrogen washout test (at 30, 60 and 120 minutes post inhalation); body plethysmography (at 60 and 120 minutes); and pharyngometry (at 30 and 120 minutes).

Participants will be asked to void their urine 30 minutes post inhalation, which we will collect a sample of. Participants will also be asked to collect their urine over the next 24 hours. If there are unable to attend to hand-in their 24-hour urine sample the following day, our research staff will collect this 24-hour-urine sample from their house/workplace the next day. Urine collected will be frozen prior to analysis.

B) Lung PHYSIOLOGY study

1. Salbutamol 1.5 micron-sized *non*-radiolabelled aerosol particles at 15 micrograms single dose delivered via the spinning-top aerosol generator (STAG), inhaled at SLOW (20-40 L/min) inhalation by patient.
2. Salbutamol 1.5 micron-sized *non*-radiolabelled aerosol particles at 30 micrograms single dose delivered via the STAG, inhaled at SLOW (20-40 L/min) inhalation by patient.
3. Salbutamol 3.0 micron-sized *non*-radiolabelled aerosol particles at 15 micrograms single dose delivered via the spinning-top aerosol generator (STAG), inhaled at SLOW (20-40 L/min) inhalation by patient.
4. Salbutamol 3.0 micron-sized *non*-radiolabelled aerosol particles at 30 micrograms single dose delivered via the STAG, inhaled at SLOW (20-40 L/min) inhalation by patient.
5. Salbutamol 6.0 micron-sized *non*-radiolabelled aerosol particles at 15 micrograms single dose delivered via the spinning-top aerosol generator (STAG), inhaled at SLOW (20-40 L/min) inhalation by patient.
6. Salbutamol 6.0 micron-sized *non*-radiolabelled aerosol particles at 30 micrograms single dose delivered via the STAG, inhaled at SLOW (20-40 L/min) inhalation by patient.

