- Spirometry will be performed at screening to determine eligibility for the study and all inclusion (section 6(i)) and exclusion criteria (section 6(ii)) assessed.
- For eligible subjects, if patients are currently prescribed Salbutamol as their 'rescue' inhaler, then this will be changed to an identical drug called Terbutaline, until they complete this research study. This will enable subjects to continue using their 'rescue' medication as they need it, because our urine measurements cannot separate Salbutamol delivered by their own regular blue 'rescue' puffer, from the Salbutamol we will deliver by our special 'fine-mist' nebuliser in the study.

Study Visits:

We will ask patients to abstain from alcohol one day before the Study Visits and for 24 hours after receiving the study treatment. In the 6 hours before each Study Visit, we will also ask patients not to use either their Terbutaline, Salmeterol (also known as a Serevent® or Seretide®), Eformoterol (also known as Oxis® or Symbicort®), Ipratropium (also known as Atrovent®) or Tiotropium (also known as Spiriva®) (if they

are prescribed these), unless patients feel they need them. There will be no change or addition to patients' treatment throughout this study by us.

There will be a minimum of a 5 day washout period between study periods.

At the Asthma Lab, subjects will be asked about any adverse effects they may have experienced. If so, the necessary action (see Section 10 below) will be undertaken). Spirometry will also be done and patients will be required to be within +/-15% of baseline Screening values before commencing study medication, to ensure lung variability is minimised.

10. Medication/IMP

Supply of drugs

The study drugs will be supplied by Royal Free Hospital (RFH), London UK to the Pharmacy of the Royal Brompton Hospital where they will be stored and dispensed.

RFH Pharmacy will assign labels to all study medication in accordance to the protocol and ICH GCP. The labels on the packages and unit medication will specify all necessary information for a correct identification of the medication boxes and individual medication units.

All study medication accountability will be performed at the Royal Brompton Hospital by members of the study team and returned /unused medication will be destroyed by the Royal Brompton Hospital Pharmacy at study closure.

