An independent scientific investigator will create a computer generated randomisation lists for the study in accordance with the protocol. Code break envelopes will be provided with copies of the randomisation code, which will be stored in the RBH Pharmacy.

11. Sample Size and Statistical Analysis

Determination of sample size

Aerosol deposition. Based on penetration index (PI) data from my previous particle-size deposition study [27], n=12 subjects will have 97% power (1- β) to detect a clinically relevant difference in means of 0.19 for PI, assuming a standard deviation of differences of 0.15, using a paired t-test with a 0.05 two-sided significance level (α). We do not have previous within patient repeatability data for PI for each individual particle size, as it is unethical to expose patients to more radioactivity than is needed. However, our data were highly significant ($p < 0.001$) in differences of PI between the three particle sizes (1.5-, 3-, 6- μm) that correlated with clinically significant differences in bronchodilator responses, and we have used the within subject SD data for PI (collectively of all 3 particles given to each patient), in the sample size calculation.

Small airway physiology. Based on Sacin and Scond data [Verbanck 1999], where MBNW responses in COPD and asthma were measured before and after pMDI salbutamol (corresponding to ΔFEV_1 19% - a clinically important difference), we calculate n=14 subjects will have 90% power (1- β) to detect a clinically relevant difference in means of 0.027 for Scond, assuming a standard deviation of differences of 0.022, using a paired t-test with a 0.05 two-sided significance level (α). Allowing for inherent biological variability for repeated measures over time, the reported intraclass correlation of Scond and Sacin is

Short title: Drug Lung Deposition in COPD

Protocol Version: 1.0; Date 20/10/2011;

Sponsor Ref: NIHR CDF

Page 9 of 14

NRES REC Ethics Number: 12/LO/0004

Eudra CT: 2011-005544-10

0.84, 0.95 respectively [Verbanck 1999], and so the sample-size required for airway physiology analysis in COPD patients is n=26 (Stata-10, Statacorp, Texas, USA).

Statistical methods

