Longitudinal analysis of paired-data will be performed within and between different groups. Data from the primary and secondary endpoints will be used to test the null hypothesis using two-way parametric analysis of covariance (ANCoVA), with factors for subject, treatment period and order. Modified paired t-tests will be undertaken using the Bonferroni method to adjust for P values and multiple comparisons between the three particle sizes. Lung deposition comparisons will be made to assess particle size deposition effects within diseased COPD patients, within healthy subjects (HS) and between disease (COPD) and health (HS). Comparisons will be made to determine the effects of inhalation flow on regional lung deposition of the three particle sizes in COPD and HS. Small airways physiology comparisons will be made between monodisperse aerosols of different particle size in COPD patients and between monodisperse and polydisperse-MDI aerosols.

12. Adverse Events

An **adverse event** (AE) is the development of an undesirable medical condition or the deterioration of a pre-existing medical condition following or during exposure to a pharmaceutical product, whether or not considered causally related to the product. An undesirable medical condition can be symptoms (e.g., nausea, chest pain), signs (e.g., tachycardia, enlarged liver) or the abnormal results of an investigation (e.g., laboratory findings).

In clinical studies, an AE can include an undesirable medical condition occurring at any time, including run-in or wash-out periods, even if no study treatment has been administered.

A **serious adverse event** (SAE) is an AE occurring during any study period (i.e., run-in, treatment, wash-out, follow-up), and at any dose of the investigational product, comparator or placebo, that fulfils one or more of the following criteria:

- results in death
- is immediately life-threatening
- requires in-patient hospitalisation or prolongation of existing hospitalisation
- results in persistent or significant disability or incapacity
- is a congenital anomaly or birth defect
- is an important medical event that may jeopardise the patient or may require medical intervention to prevent one of the outcomes listed above

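### Pre-dose spirometry taken at every visit serves only as a ±15% entry gate; the plan names no pre-dose covariate for the post-dose spirometry outcomes, so some removable visit-to-visit variation can stay in the error

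*Combined protocol and SAP*

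**What the plan says.** Section 9 (Study Visits) places spirometry before dosing at each visit: "Spirometry will also be done and patients will be required to be within +/-15% of baseline Screening values before commencing study medication". The stated purpose is "to ensure lung variability is minimised". The same section asks patients to withhold bronchodilators for 6 hours beforehand, "unless patients feel they need them".

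Section 7 gives the post-dose schedule for both studies: "spirometry, impulse oscillometry, and multi-breath nitrogen washout test (at 30, 60 and 120 minutes post inhalation". Section 4 makes spirometry an outcome: "The secondary outcome measures for both studies are: analysis of the lung physiology (MBNW, Impulse oscillometry (IOS), spirometry, body plethysmography".

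Section 11 (Statistical methods) applies one model to primary and secondary endpoints: "analysis of covariance (ANCoVA), with factors for subject, treatment period and order". It adds: "Modified paired t-tests will be undertaken using the Bonferroni method to adjust for P values and multiple comparisons between the three particle sizes". No covariate is named. The section does not say whether spirometry is analysed as the post-dose value, as absolute change or as percent change, or which of the three post-dose times is used.

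**The concern.** Both studies are crossovers with visits at least 5 days apart. A patient's airway calibre on the day can differ between visits, and the as-needed exception to withholding is one possible source of that.

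The listed terms do not deal with it. Subject removes stable differences between patients, including the Screening level. Period and order remove average time and sequence effects. None removes one patient's departure on one day. The gate truncates such departures but leaves whatever lies within ±15%.

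The pre-dose value measures that departure directly, on the same scale as the outcome. If it is left out, treatment contrasts for spirometry may be less precise than the collected data allow. The unstated outcome scale also leaves several analyses open to choice after the results are seen.

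**Working it through.** The plan gives no SD, target difference or power for spirometry, so there is no figure of its own to reproduce. The check asks what a same-visit covariate would gain or cost.

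**Inputs from the documents.** Physiology study: 26 COPD and 13 asthma patients, 7 treatments. Deposition study: 12 per group. Both 6 and 7 visits are shown for it, because section 3 gives 6 radiolabelled visits and section 7 lists 7 treatments.

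**Assumed.** r, the within-patient, between-visit correlation of pre-dose with post-dose spirometry, and one post-dose value per visit.

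**Step 1: residual degrees of freedom** with fixed subject, period and treatment, for n patients and p visits: df = np − 1 − (n − 1) − 2(p − 1).
- 26 × 7: 182 − 1 − 25 − 12 = 144
- 13 × 7: 91 − 1 − 12 − 12 = 66
- 12 × 7: 84 − 1 − 11 − 12 = 60
- 12 × 6: 72 − 1 − 11 − 10 = 50

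**Step 2: variance of a treatment contrast, with versus without the covariate.** Ratio = (1 − r²) × (1 + 1/(df − 2)). The second term is the cost of estimating the slope. For 26 × 7 at r = 0.5: 0.75 × (1 + 1/142) = 0.755.

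| Design | r = 0 | r = 0.1 | r = 0.3 | r = 0.5 |
|---|---|---|---|---|
| 26 × 7 | 1.007 | 0.997 | 0.916 | 0.755 |
| 13 × 7 | 1.016 | 1.005 | 0.924 | 0.762 |
| 12 × 7 | 1.017 | 1.007 | 0.926 | 0.763 |
| 12 × 6 | 1.021 | 1.011 | 0.929 | 0.766 |

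A simulation with random treatment order (2,500 to 4,000 trials per design) agreed. At r = 0, 0.3 and 0.5 the ratio was 1.01, 0.91 and 0.75 for 26 × 7, and 1.02, 0.92 and 0.77 for 12 × 6. Mean estimates stayed within about 0.012 SD of zero, so no bias appeared.

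**Step 3: break-even.** Setting the ratio to 1 gives r² = 1/(df − 1), so |r| = 0.084, 0.124, 0.130 and 0.143 for the four designs. Charging the lost degree of freedom as well (alpha 0.05/3, 90% power) gives 0.084, 0.127, 0.133 and 0.147.

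**Step 4: effect of the gate on r.** Suppose Screening and visit values share a within-patient SD of 4, 6, 8 or 10% (assumed), and visits outside ±15% are redrawn. An ungated r of 0.5 then falls to about 0.49, 0.46, 0.41 or 0.36, and 1 − r² becomes 0.76, 0.79, 0.83 or 0.87. An ungated 0.3 falls to about 0.30, 0.27, 0.24 or 0.21, still above every break-even value in step 3.

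**Step 5: outcome scale.** At equal SDs, unadjusted change has variance proportional to 2(1 − r), against 1 − r² for the covariate model. The ratio is 2/(1 + r): 1.54 at r = 0.3 and 1.33 at r = 0.5. With the covariate in the model, post-dose value and absolute change differ only by a multiple of that covariate, so they give the same treatment contrast. Percent change divides by the pre-dose value and does not share this property.

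**The case against.** The strongest reply is that the plan may already intend this. It names an analysis of covariance and then lists factors. A list of factors need not include covariates, and treatment itself is missing from it, so the list is not the full model. That stands: the text does not exclude a covariate, and the gap is one of specification. But the text does not supply a covariate either, and the paired t-tests as described have none.

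A second reply is that no consequence follows from the documents' own figures. r is unknown, and at r = 0.1 adjustment is about neutral with 26 patients and slightly harmful with 12 or 13. That also stands, and it is why the point is optional.

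A reader might infer more than the documents support:
- **That the gate lets through noise larger than the effect of interest.** Two visits at 85% and 115% of Screening both pass, a gap of 30% of Screening, and section 11 cites an FEV1 change of "19% - a clinically important difference". These are unlike quantities: an extreme permitted gap between two visits, and a response from before to after treatment. Before gating, a gap that wide would occur in about 0.04%, 0.8% or 3.4% of visit pairs at assumed SDs of 6, 8 or 10%.
- **That adding the covariate makes the outcome scale irrelevant.** This is true for absolute change but not for percent change.
- **That the primary endpoints suffer.** Nothing here shows a gain for penetration index, Sacin or Scond. The text lists nitrogen washout only after inhalation, and the flowchart it refers to was not available to check.

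**Conclusion.** The point holds as an optional improvement to the analysis of a secondary outcome in both studies. Pre-dose spirometry is collected at every visit, its only stated use is the gate, and no stated model term removes a patient's visit-specific deviation.

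The loss is of precision. Treatment order is randomised, so the comparison is not biased, and the documents give no basis for claiming a power shortfall. The gain rests on an assumed r and on one post-dose value per visit. The trade is lopsided in favour of adjustment: a small loss if r is near zero, and a useful gain once r is clearly above break-even. Confidence in the size is moderate, because r is not documented and the gate may lower it.

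**What to change.** In Statistical methods:
- Prespecify same-visit pre-dose FEV1, or the matching pre-dose value for any other spirometry outcome, as a covariate for the post-dose spirometry outcomes, with fixed subject, period and treatment.
- Say whether the model applies at each of 30, 60 and 120 minutes or to a named summary.
- Take the Bonferroni-adjusted particle-size contrasts for these outcomes from that model.
- Say what order means. If it means sequence, fixed subject absorbs it.
- State the outcome scale. Post-dose value and absolute change are interchangeable once the covariate is in; percent change is not.
- If no covariate is intended, say so and still state the scale.

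The cost is wording and one residual degree of freedom (144 to 143 at 26 × 7; 50 to 49 at 12 × 6). If r is 0, contrast variance rises by 0.7% to 2.1% across those designs. No visit, procedure or measurement is added.

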The single-centre study will be carried out at the Asthma Lab, Royal Brompton Hospital and National Heart and Lung Institute, London, UK. Patients will be recruited from: Asthma Lab NHLI, Respiratory outpatients of the Royal Brompton and Harefield NHS Foundation Trust, St Mary's Hospital part of Imperial College NHS Trust, Local GP Practices and from our current patient Asthma Lab database from local GP Practices.

The study will recruit;

Lung DEPOSITION study: 12 mild-moderate COPD patients, 12 healthy subjects

Lung PHYSIOLOGY study: 26 mild-moderate COPD patients, 13 mild-moderate asthmatic patients

6. Inclusion criteria

COPD patients, either male or female, over the age of 40 with a clinical diagnosis of COPD with airflow obstruction (FEV1/FVC<0.7) and post-bronchodilator FEV1>50% predicted, gas trapping (on lung volume testing), and decreased carbon monoxide transfer factor.

Healthy subjects will be non-smokers (or ex-smokers stopped 5 years ago), will have no respiratory disease, normal spirometry and be age-matched to the COPD patients.

Asthmatic subjects, either male or female, over the age of 18 with a clinical diagnosis of Asthma with airflow obstruction (FEV1/FVC<0.7).

Capable of giving informed consent.

(ii) Exclusion Criteria

As a result of the medical interview, physical examination or screening investigations, the Physician Responsible considers the volunteer unfit for the study.

Oral corticosteroids taken within last month, as this can affect the breathing response and signifies that their condition needs to be controlled better.

Current involvement (or involvement in the last 4 weeks) in clinical trials assessing investigational medicinal products.

Previous adverse reaction to short or long acting β 2 agonist.

Any subject with a contraindication to taking inhaled beta-2 adrenoceptor agonists (especially Salbutamol) as listed in the British National Formulary will not be entered into this study.

Those who have experienced an acute respiratory exacerbation requiring emergency room treatment and/ or hospitalisation within last four weeks as this signifies that their condition needs to be controlled better.

Pregnant or breast-feeding women.

Subjects unable to give Informed Consent.

7. Study Plan and Treatments (see also 'FLOWCHART')

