All patients will receive all study treatments in each study. All treatments will be via the inhaled route of administration in each study. Treatments (all 'one-off' dosing) will only be taken while the patient is at the investigator site and there will be no treatments to take home with them.

Patients will randomly receive the following treatments (see also page 1 FLOWCHART document);

A) *Lung DEPOSITION study*

1. Salbutamol 1.5 micron-sized radiolabelled (*) aerosol particles at 30 micrograms single dose delivered via the spinning-top aerosol generator (STAG), inhaled at SLOW (20-40 L/min) inhalation by patient.
2. Salbutamol 3.0 micron-sized radiolabelled (*) aerosol particles at 30 micrograms single dose delivered via the STAG, inhaled at SLOW (20-40 L/min) inhalation by patient.
3. Salbutamol 6.0 micron-sized radiolabelled (*) aerosol particles at 30 micrograms single dose delivered via the STAG, inhaled at SLOW (20-40 L/min) inhalation by patient.
4. Salbutamol 1.5 micron-sized radiolabelled (*) aerosol particles at 30 micrograms single dose delivered via the STAG, inhaled at FAST (>60 L/min) inhalation by patient.
5. Salbutamol 3.0 micron-sized radiolabelled (*) aerosol particles at 30 micrograms single dose delivered via the STAG, inhaled at FAST (>60 L/min) inhalation by patient.
6. Salbutamol 6.0 micron-sized radiolabelled (*) aerosol particles at 30 micrograms single dose delivered via the STAG, inhaled at FAST (>60 L/min) inhalation by patient.
7. Salbutamol non-radiolabelled aerosol particles at 200 micrograms single dose delivered via a pMDI the STAG, inhaled at SLOW (20-40 L/min) inhalation by patient.

A) During the LUNG DEPOSITION study, participants will receive 6 treatments of 'fine-mist' monodisperse salbutamol of 1.5, 3.0 and 6 μ m micron sized aerosols radiolabelled with 99MTechnetium that will each be inhaled at a SLOW and a FAST inhalation flow by the patient (each treatment 30 microgram dose). Participants will also receive non-radiolabelled 'coarse-mist' inhaler of salbutamol from a pMDI (200 micrograms dose). 'Fine-mist' monodisperse salbutamol aerosols will be generated using a spinning-

6
top disc aerosol generator (STAG) as previously described by [name] et al (AJRCCM 2005). The operator will be blinded to the particle size being administered.

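### The 97% power for penetration index is calculated at an unadjusted 0.05, while the particle-size comparisons are Bonferroni-adjusted and no power is given at that level

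*Combined protocol and SAP*

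**What the plan says.** Section 4 makes PI the primary endpoint of the deposition study, to show how regional deposition differs by particle size.

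Section 11, Determination of sample size (aerosol deposition paragraph), states that "n=12 subjects will have 97% power" for a mean difference of 0.19 in PI, "assuming a standard deviation of differences of 0.15, using a paired t-test with a 0.05 two-sided significance level". On the source of the 0.15, the same paragraph adds: "we have used the within subject SD data for PI (collectively of all 3 particles given to each patient), in the sample size calculation".

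Section 11, Statistical methods, tests the null hypothesis by "two-way parametric analysis of covariance (ANCoVA), with factors for subject, treatment period and order". It then says: "Modified paired t-tests will be undertaken using the Bonferroni method to adjust for P values and multiple comparisons between the three particle sizes". It does not define *modified*.

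Section 7 gives the three sizes at two flows, as aerosols "that will each be inhaled at a SLOW and a FAST inhalation flow by the patient", so there are six radiolabelled treatments per subject. Section 5 recruits "12 mild-moderate COPD patients, 12 healthy subjects" for this study.

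**The concern.** The power sentence describes one paired t-test at 0.05. The analysis text describes comparisons among three sizes, which means three pairs and 0.05/3 = 0.0167 for each if they form one family. The 97% is the only power figure given for PI, and it belongs to a significance level that the plan does not use for those comparisons.

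The size of the gap depends on two things the plan leaves open. One is the error term behind *modified*: the differences of each pair alone, or the pooled residual of the model. The other is the family: sizes compared at each flow, over both flows together, or averaged over flows.

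All of these figures rest on 0.15, which the sample-size paragraph describes in two ways that are not the same quantity. A within-subject SD is smaller than the SD of paired differences by a factor of √2.

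**Working it through.** **Inputs** (Section 11, sample size): n = 12; difference δ = 0.19; SD of paired differences s = 0.15; two-sided tests.

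**Formula.** Noncentrality λ = (δ/s)·√n. Power is the probability that a noncentral t variable with the stated degrees of freedom (df) and λ falls beyond ±t(1 − α/2, df).

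**1. The plan's own figure.** λ = (0.19/0.15)·√12 = 4.388. With 11 df and α = 0.05 the critical value is 2.201 and power is **97.8%**. The stated 97% reproduces.

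**2. Bonferroni level, ordinary paired t-tests.** α = 0.05/3 = 0.0167, 11 df, same λ. The critical value rises to 2.820 and power per comparison is **91.9%**.

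**3. Bonferroni level, pooled model error (assumption about *modified*).** λ is unchanged if the SD of differences stays at 0.15. Only the df change.

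| Error term | df | Power at 0.05/3 |
|---|---|---|
| Three sizes at one flow, subject and treatment removed | (3 − 1)(12 − 1) = 22 | 95.5% |
| Six treatments, subject, treatment and period removed | 71 − 11 − 5 − 5 = 50 | 96.9% |
| Six treatments, period not removed | 71 − 11 − 5 = 55 | 97.0% |

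**4. The comparison family.** If the three pairs at both flows form one family of six (assumption), α = 0.05/6 = 0.0083. Ordinary paired t-tests (critical value 3.208) then give **85.0%**. If instead sizes are averaged over the two flows and 0.15 is the SD at one flow (assumptions), the SD becomes 0.15·√((1 + r)/2), where r is the correlation between the two flows' differences. At 0.05/3 with 11 df, power is 99.8%, 97.6%, 95.1% and 93.2% for r = 0, 0.5, 0.75 and 0.9.

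**5. The meaning of 0.15.** If it is a within-subject SD (assumption), the SD of differences is 0.15·√2 = 0.212 and λ = (0.19/0.212)·√12 = 3.10. Ordinary paired t-tests then give **80.6%** at 0.05 and **61.9%** at 0.05/3.

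All figures are power for a single comparison, not for all comparisons together.

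**The case against.** The strongest reply is that little is lost. The statistical methods start from a model with subject, period and order, so an ordinary 11-df t-test is not the obvious meaning of *modified*. On pooled error the power is 95.5% to 97.0% against a stated 97%, a shortfall of at most about two points. If the overall model test of size is the main test at 0.05, its power is about 96% (assuming one flow, extreme sizes 0.19 apart, the middle size halfway, error variance 0.15²/2 and 20 to 22 df). The wording of the Bonferroni sentence also favours three comparisons over six.

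Much of this stands. It means that 92% cannot be put forward as the one correct figure. It does not remove the mismatch: the plan neither says which test applies nor gives power for it.

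Two stronger readings are tempting. A reader might infer from the 97% that the plan can afford to lose three subjects, since 9 completers still give 91% at 0.05. A reader might equally infer that 12 is now the bare minimum, since with ordinary paired t-tests at 0.0167 it is the smallest number that gives 90%. The documents support neither. They claim no such margin and set no 90% target for PI; the 90% in Section 11 belongs to Scond in the physiology study.

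**Conclusion.** The point holds as a minor inconsistency between the sample-size text and the analysis text. The 97% is correct for its stated inputs but is not the power of the planned Bonferroni-adjusted comparisons. For three comparisons on the stated SD, without averaging over flows, that power is about 92% (ordinary paired t-tests) to about 97% (pooled error). A family of six with ordinary paired t-tests would give 85%.

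The mismatch in significance level does not show that 12 subjects are too few, and a reader should not conclude that it does. Equally, it cannot be said that power stays above 90% on every reading, because the family of six falls below that.

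The largest uncertainty is the SD. The plan labels 0.15 an SD of differences, and the figures above take it at its word. A reader might infer from the mention of within-subject SD data that the calculation is wrong by √2. The text does not establish that, because the phrase may only name the data source. It does need confirming, since the power would otherwise be 80.6% at 0.05 and 61.9% at 0.0167 with ordinary paired t-tests.

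**What to change.** In Section 11:

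- **Restate the PI power at the Bonferroni level for the test that will be used.** For ordinary paired t-tests and three comparisons, for example: *n=12 gives 92% power per comparison to detect a difference of 0.19 in PI between two particle sizes (SD of paired differences 0.15, two-sided paired t-test at 0.0167).* If the pooled model error is used, give the figure for its df instead (95.5% to 97.0% above).
- **Name the error term and the family.** Say what *modified* means, and whether sizes are compared at each flow (and then whether the adjustment covers three or six tests) or averaged over flows.
- **Confirm in the same sentence that 0.15 is the SD of paired differences.** If it is a within-subject SD, recalculate and restate the power.

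The cost is two or three sentences, and the stated power may become somewhat less favourable. On the stated SD, no extra subjects and no change to the conduct of the study are proposed.
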